15.4 Significance Testing

The secondary (efficacy) outcome will be evaluated using a two-sided test on the significance of the treatment parameter in the proposed model with a type I error rate of 5%. No attempt will be made to control family-wise type I error rate when testing for CUD and MUD participants. No other hypothesis testing will be performed on the primary or secondary outcomes.

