15.3.2 Secondary (Efficacy) Outcome

The secondary (efficacy) outcome will be analyzed with a generalized linear mixed model approach to adjust for correlation between UDS from the same participants and to provide conditional interpretation of the treatment effect. The model will include fixed effects for treatment, MDE, week, and site and a random effect for participant. It is important to note that a binary response of negative UDS, for each UDS provided by each participant, will be used as the outcome as opposed to just their percentage of negative UDS. The model used still allows inference on the overall probability of a negative weekly UDS during the treatment period. Additionally, week will enter the model as a categorical variable to allow greater flexibility on the effect of week.

The assessment of the significance of the treatment will be done by testing the significance of the treatment parameter at the 0.05 significance level. The treatment effect will be measured by an odds ratio with an associated 95% confidence interval. The corresponding shell SAS code is provided below.

```
proc glimmix data = dat method = quad;
  class site week participant;
  model y(event = '1') = trt mde week site / dist = binary link
  = logit;
  random intercept / subject = participant;
run;
```

dat is a dataset with one row per weekly UDS per participant. y is the a binary variable with a value of 1 indicating the UDS for that participant was negative, trt is a binary variable with a value of 1 indicating real rTMS and 0 indicating sham rTMS, mde is a binary variable with a value of 1 indicating the presence of MDE, week is the study week, and site is a categorical variable containing which of the sites each participant was enrolled in.

In the event that the estimate of the variance component related to the within participant correlation is so close to 0 that it causes the overall covariance matrix to not be positive definite, the model will be refit without the random effect for the correlation within participant. This is accomplished simply by removing the line starting with random in the shell SAS code shown above.

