7.5 Analyses of the Secondary Outcome Measures

The secondary (efficacy) outcome will be analyzed in the ITT population (defined in Section 3.1.3) with a generalized linear mixed model approach to adjust for correlation between UDS from the same participants and to provide conditional interpretation of the treatment effect. The model will include fixed effects for treatment, major depressive episode (MDE), week, and site and a random effect for participant. It is important to note that a repeated measure, binary response of negative UDS, for each UDS provided by each participant, will be used as the outcome, as opposed to the total percentage of negative UDS. The model used still allows inference on the overall probability of a negative weekly UDS during the treatment period. Additionally, week will enter the model as a categorical variable to allow greater flexibility on the effect of week. Section 7.9 describes missing data handling procedures for the secondary outcome sensitivity analyses.

The assessment of the significance of the treatment will be done by testing the significance of the treatment parameter at the 0.05 significance level. The treatment effect will be measured by an odds ratio with an associated 95% confidence interval. The corresponding SAS code is provided below:

```
proc glimmix data = data method = quad;
  class site week participant;
  model y(event = '1') = trt mde week site / dist = binary link
    = logit solution;
  random intercept / subject = participant;
run;
```

where:

- data is a dataset with one row per weekly UDS per participant for the specified primary substance of use,
- y is the binary variable with a value of 1 indicating the UDS for that participant was negative and 0 indicating positive UDS result,
- trt is a binary variable with a value of 1 indicating active rTMS and 0 indicating sham rTMS,
- mde is a binary variable with a value of 1 indicating the presence of MDE,
- week is the study week (1 – 8, categorical), and
- site is a categorical variable containing which of the sites each participant was enrolled in.

In the event that the estimate of the variance component related to the within participant correlation (i.e., the ICC for UDS) is so close to 0 that it causes the overall covariance matrix to not be positive definite, the model will be refit without the random effect for the correlation within participant. This is accomplished simply by removing the random effect.

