9.0 SIGNIFICANCE TESTING AND MULTIPLICITY

The secondary (efficacy) outcome will be evaluated using a two-sided test on the significance of the treatment parameter in the proposed model with a Type I error rate of 5%. No attempt will be made to control family-wise Type I error rate when testing for CUD and MUD participants. No other hypothesis testing is planned for the primary or secondary outcomes.

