	120	0.086
	130	0.083
	140	0.080
	150	0.077
	160	0.075
75%	200	0.067
	400	0.048
	40	0.128
	60	0.106
	80	0.093
	100	0.083
	110	0.080
	120	0.076
	130	0.073
	140	0.071

Table 5: Re-estimation Power Analysis Results for Secondary (Efficacy) Outcome

		Power n per Use Disorder Subgroup	
Probability of Negative UDS in Sham Arm	Odds Ratio	n = 50	n = 70
-0.025	1.5	14%	13%
	2.0	25%	36%
	3.0	67%	82%
Observed Probability	1.5	15%	20%
	2.0	42%	56%
	3.0	86%	96%
+0.025	1.5	19%	27%
	2.0	54%	70%
	3.0	95%	99%

The second sample size re-estimation conducted in December 2023 followed the same methods with current data used to estimate the UDS standard deviation and probability of success. The report provided to NIDA CCTN February 13, 2024 contained the following results:

1. The target sample size in each use disorder group required in order to detect clinically meaningful effect size of 2.0 with at least 80% power is 92.
2. With 52 participants, the number of participants recruited in the cocaine use disorder group as of database freeze December 15, 2023, there is at least 80% power to detect an odds ratio of 3.0.

It was determined that with the number of participants recruited in each use disorder group, assuming the recruitment rate in that group as of late December 2023, it would take approximately 14 months to achieve the sample size in the cocaine use disorder group to be able to detect the clinically meaningful effect size. The protocol was not amended, and NIDA CCTN recommended the study recruitment not be extended.

Table 6: Power to detect OR=2.0 for various sample sizes

N per Group	Power
52	53.1%
80	73.2%
90	79.4%
91	79.7%
92	81.6%

Table 7: Power for n=52 and various odds ratios and probabilities of a negative UDS

Probability of Negative UDS	Odds Ratio	Power
-0.025	2	40%
	3	85%
Observed	2	53%
	3	94%
0.025	2	63%
	3	97%

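### At the plan's own inputs the printed efficacy model has a type I error of about 6% with 80 participants, not the stated 5%, and its 95% intervals cover about 94%

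*Protocol*

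**What the plan says.** Protocol 15.4 states that the efficacy outcome is "evaluated using a two-sided test on the significance of the treatment parameter in the proposed model with a type I error rate of 5" per cent. SAP 9.0 repeats this: "using a two-sided test on the significance of the treatment parameter in the proposed model with a Type I error rate of 5" per cent.

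Protocol 15.3.2 defines the model: "The model will include fixed effects for treatment, MDE, week, and site and a random effect for participant". The code is "proc glimmix data = dat method = quad" with "random intercept / subject = participant", and SAP 7.5 prints the same call ("proc glimmix data = data method = quad"). Neither listing sets denominator degrees of freedom or a small-sample correction. If the participant variance collapses to zero, "the model will be refit without the random effect for the correlation within participant". The model is run once in the cocaine group and once in the methamphetamine group.

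The power simulation in Protocol 15.2.2 uses 80 participants per group and odds ratios of 2 to 5. The re-estimation in SAP 11.1 adds 1.5. No run at an odds ratio of 1, and no interval coverage, is reported.

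SAP 7.10, added after database lock, keeps this model wherever it converges and gives reliable results. Otherwise it moves to a model with treatment and a participant random effect only, and then to summary statistics.

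**The concern.** Treatment varies only between participants, so the information on it is limited by the number of participants in each group and not by the number of urine screens. Six between-participant parameters are fitted: intercept, treatment, MDE and three site contrasts. Maximum likelihood makes no allowance for estimating them, so it tends to understate the participant variance and hence the standard error of the treatment effect. A near-normal critical value adds to this.

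These are the only tests planned on the secondary outcome, and the primary outcome has none. Protocol 5.2 wants the effect size in order to inform later trials. A test that rejects a little too often, with an interval a little too narrow, would pass both faults to the next design. Because the plan never simulated the null, nothing in it would reveal them.

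**Working it through.** **Inputs from the documents.** N = 80 per analysis, eight weekly screens, sham probability 0.36 (also 0.26 and 0.46), and ICC 0.25 or 0.5 with random-effect SD 1.05 or 1.81 (Protocol 15.2.2). Four sites and 1:1 allocation stratified by site and MDE (15.1.4, 15.2.3). N = 52 for cocaine at the December 2023 freeze (SAP 11.1.1).

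**Assumptions.** MDE prevalence 0.3, blocks of 4, equal sites, and all screens present (as in the plan's simulation). The code's default degrees of freedom are taken as residual-type, screens minus participants minus seven week contrasts: 640 - 80 - 7 = 553 and 416 - 52 - 7 = 357. Between-participant degrees of freedom are N - 6: 74 and 46.

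**Method.** The printed model was fitted by full maximum likelihood with 41-point quadrature, standard errors from the observed information, and the plan's refit rule.

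**Step 1: reproduce Protocol Table 8 (sham 0.36, N = 80; 6,000 data sets per cell).**

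| ICC | Odds ratio | Stated | Reproduced |
|---|---|---|---|
| 0.5 | 2 | 35% | 34.9% |
| 0.5 | 3 | 69% | 68.0% |
| 0.5 | 4 | 86% | 86.2% |
| 0.5 | 5 | 94% | 94.0% |
| 0.25 | 2 | 67% | 66.9% |
| 0.25 | 3 | 96% | 96.5% |

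Five further cells at N = 40, 60 and 100 also agree within 2 points.

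**Step 2: set the odds ratio to 1 (15,000 to 40,000 data sets per cell; Monte Carlo SE 0.1 to 0.2 points).**

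| N | Type I error | 95% interval coverage | Mean SE below true SD by |
|---|---|---|---|
| 80 | 5.7% to 6.3% | 93.7% to 94.3% | 3% to 5% |
| 52 | 6.3% to 6.9% | 93.2% to 93.7% | 5% to 6% |

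A z test or a likelihood-ratio test gives nearly the same. Coverage away from the null is similar: 93.9% to 94.3% at N = 80 for odds ratios 2 to 5, and 93.7% at N = 52 for odds ratio 3.

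**Step 3: hand check.** In one cell at N = 80 the mean SE is 0.292 against a true SD of 0.303, a ratio of 0.964. The cut-off of 1.964 then acts like 1.964 x 0.964 = 1.893, and the two-sided normal tail beyond 1.893 is about 5.8%. At N = 52, 0.358/0.381 = 0.940; 1.967 x 0.940 = 1.848; the tail is about 6.5%.

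**Step 4: split the cause, and test a correction (sham 0.36; 15,000 data sets per cell).**

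| N, ICC | Default df | N - 6 df | N - 6 df and SE x sqrt(N/(N - 6)) |
|---|---|---|---|
| 80, 0.25 | 6.15% | 5.80% | 4.93% |
| 80, 0.5 | 6.11% | 5.73% | 4.79% |
| 52, 0.25 | 6.81% | 6.31% | 4.87% |
| 52, 0.5 | 6.93% | 6.29% | 4.83% |

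Degrees of freedom account for 0.35 to 0.64 points, roughly a third of the excess; the variance estimate accounts for the rest. The factor is sqrt(80/74) = 1.040 or sqrt(52/46) = 1.063. Multiplied by the t cut-offs 1.993 and 2.013, it gives effective cut-offs of 2.07 and 2.14. The simulated cut-offs that give exactly 5% are about 2.06 and 2.13.

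**Step 5: sensitivity under the null.**
- 8% dropout per week and a 40/30/20/10 site split (both assumed): 6.1% at N = 80; 6.3% to 6.7% at N = 52.
- Simplified model of SAP 7.10.1: 5.2% to 5.4% at N = 80; 5.2% to 5.8% at N = 52.
- Low probability and near-zero correlation (p = 0.07, SD = 0.25, both assumed; latent ICC = 0.0625/(0.0625 + 3.29) = 0.02): 5.1% at N = 80; 4.8% at N = 52.
- Same p with SD 1.05 or 1.81: 6.1% to 6.8% at N = 80; 7.1% to 7.3% at N = 52.

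The last two rest on about 5,000 data sets each (Monte Carlo SE 0.3 to 0.4 points).

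**The case against.** The strongest objection concerns N = 52. That count belongs to a re-estimation that had replaced 0.36 and the planning ICCs with observed values, which are not printed. SAP Table 7 suggests the observed probability was far lower: at odds ratio 2, moving it by 0.025 either way takes power from 53% to 40% or 63%. In Protocol Table 8, moving 0.36 by 0.10 changes power by at most 3 points. Taking p near 0.07 and SD near 0.25 gives 38%, 53% and 62% against the printed 40%, 53% and 63%, and under those values there is no inflation. This stands as a limit on the claim. It does not remove it, because the SD is not printed and the same p with the planning SDs gives more than 7%.

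Second, SAP 7.10 reports that the planned models could not be completed as intended, and the fallback drops the MDE and site terms. Where it applies, most of the excess goes. But 7.10.1 still puts the full model first whenever it is reliable.

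Third, this is a secondary outcome in a pilot that SAP 11.1.1 says is not powered for efficacy, and a 0.05 level for a Wald test is ordinarily read as nominal. That is fair on importance. Even so, both documents state the rate as a property of the test, and it is not met at their own inputs.

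A reader might infer that the cocaine analysis in fact ran at about 7%. The documents do not support that: 52 is a freeze count and not a stated final N, the correlation is unknown, and the model finally used may be the simpler one. A reader might also blame the software's default degrees of freedom. That default is not stated in the documents, and correcting it alone leaves 5.7% to 6.3% in Step 4.

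**Conclusion.** The point holds in a limited form. At the planning inputs and N = 80, the size is about one percentage point above the stated 5% and coverage about one point below 95%. At N = 52 with the planning ICCs, the excess is 1.3 to 1.9 points. The result rests on the full model being used and on real within-participant correlation, which the plan itself assumes at 0.25 to 0.5. The assumed MDE prevalence, block size and site split are not in the documents, though dropout and unequal sites made little difference.

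The absence of family-wise control across the two groups is declared openly and is a separate matter. The finding does not invalidate the efficacy analysis. It means the stated 5% was never checked and is slightly optimistic.

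**What to change.** In SAP 7.5, wherever 7.10.1 retains the full model, and in Protocol 15.3.2, report the treatment p-value and odds-ratio interval with `ddfm=bw` and with the standard error multiplied by sqrt(N/(N - 6)), where N is the number of participants in that model. Show this beside the prespecified Wald result and label it as added after database lock.

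At minimum, in Protocol 15.4 and SAP 9.0, describe 5% as nominal and give the simulated size and coverage.

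**Cost.** No new data are needed. Intervals on the log-odds scale widen by 2.07/1.964 = 1.05 (about 5%) at N = 80 and 2.14/1.967 = 1.09 (about 9%) at N = 52. Power at odds ratio 4, N = 80, ICC 0.5 falls from 86.5% to 85.8% with `ddfm=bw` alone, and a little further with the standard-error factor.

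A stratified re-randomisation p-value may be added as a sensitivity analysis. It should not replace the model-based test: it would leave the interval uncorrected, and substituting it now would be a post-lock change of method.

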15.5 Types of Analyses

15.5.1 Additional Feasibility Analysis

The primary analysis method used for the primary (feasibility) outcome will be completed over all 160 participants. Additional analysis may include estimating the feasibility outcome percentage separately for both CUD and MUD participants, separately for real and sham rTMS, as well as separately for the four combinations of the two factors. Testing may be performed using fisher's exact test at an 0.05 significance level to determine if there are differences in the percentages across or within the factors, though emphasis is placed on estimation and 95% confidence intervals.

15.5.2 Additional Efficacy Analysis

In preparation to assist in designing future larger trials of efficacy, estimates of the MDE, site and participant effects may be explicitly given. For the participant effect, this will likely be an estimate of the variance in the outcome attributed to the within participant correlation.

Additional supportive analysis of the secondary (efficacy) outcome will be examining if treatment effect varies depending on study week. This can be accomplished by introducing an interaction between week and treatment in the proposed model and examining the significance of the joint or type III test on that interaction. If significant, estimates of treatment effect based on study week can be presented.

15.5.3 Interim Analysis

A DSMB will monitor the progress of the trial. No classical interim analyses relating to futility or sample size re-estimation will be implemented in this pilot study. Safety halting rules are presented in the Study Halting Rules section elsewhere in the protocol.

15.5.4 Exploratory Analysis

Recall the exploratory outcomes may include, and are not limited to

- Other feasibility measures:
 - Percent of participants that complete at least 75% of daily monitoring
 - Percent of participants that complete all follow-up visits
- Self-reported cocaine and methamphetamine use (Timeline Follow-Back)
- Cocaine and/or methamphetamine craving (VAS)
- Depression/anxiety symptoms (Hospital Anxiety and Depression Scale)

- Sleep quality (Actigraphy, Pittsburgh Sleep Quality Index)
- Quality of life (HRQOL-4 quality of life assessment)
- Resting connectome biomarkers measured by EEG
- Differences in outcomes based on number of CBT sessions completed
- Impact of handedness on treatment outcome
- Impact of changes in motor threshold over treatment course on treatment outcome

The other feasibility measures may be analyzed analogously to the primary (feasibility) outcome. The other exploratory outcomes may be summarized and analyzed as appropriate for the type of outcome, such as fisher exact tests and/or logistic regression models for binary outcomes and non-parametric tests of mean/median differences and other types of regression models for ordinal or continuous outcomes.

15.6 Missing Data and Dropouts

As defined, the primary (feasibility) outcome will have no missing data. Participants that drop out early will still be evaluated as to whether they attended at least 20 rTMS sessions.

The secondary (efficacy) outcome is expected to have missing data, specifically UDS results. The proposed analysis model takes into account all available data and missing data are assumed to be missing at random (a weaker assumption than missing completely at random). That is, missingness is allowed to depend on observed covariates. As such, the prespecified analysis method does not need missing data to be imputed or handled in some special way. That being said, alternative methods of handling missing data may be considered as sensitivity analyses. Some specific examples may involve imputing a negative UDS in place of missing if that UDS is immediately surrounded by negative UDS, imputing missing UDS results based on self-reported use, or imputing all missing UDS as positive. More technical methods incorporating a missing not at random assumption may also be considered.

15.7 Demographic and Baseline Characteristics

Baseline demographic and clinical variables will be summarized for participants enrolled in the active medication phase of the trial. Descriptive summaries of the distribution of continuous baseline variables will be presented with percentiles (median, 25th and 75th percentiles), and with mean and standard deviation. Categorical variables will be summarized in terms of 'frequencies and percentages.

15.7.1 Subgroup Analyses

Per NIH policy, subgroup analyses will be implemented to assess whether sex, race, and/or ethnicity are feasibility or effect modifiers. The primary outcome percentage will be estimated in each demographic subgroup. The secondary (efficacy) outcome results will be presented and tested (as applicable) within each demographic subgroup by including interactions with treatment assignment in the model.

15.8 Safety Analysis

AEs, SAEs and UADEs, will be summarized by body system and preferred term using MedDRA codes (per The Medical Dictionary for Regulatory Activities). AEs will be presented as: (1) the number and proportion of participants experiencing at least one incidence of each event overall; and (2) the total number of each event overall in tabular form. Listings of SAEs /UADEs will be sorted by system organ class (SOC), and preferred term (PT). Detail in these listings will include severity, relationship to study medication(s), and action taken, as available.

16.0 REGULATORY COMPLIANCE AND SAFETY

16.1 Investigational Device Exemption Applicability

This study represents an investigation of a device other than a significant risk device, and as such will be considered an approved IDE application subject to the abbreviated IDE regulations as stated in 21 CFR 812.2(b). The Sponsor will obtain and maintain IRB approval accordingly, and will be subject to all applicable reporting requirements.

16.2 Statement of Compliance

This trial will be conducted in accordance with the current version of the protocol, in full conformity with the ethical principles outlined in the Declaration of Helsinki, the Protection of Human Subjects described in the International Council for Harmonisation Good Clinical Practice (GCP) Guidelines, applicable United States (US) Code of Federal Regulations (CFR), the NIDA Terms and Conditions of Award, and all other applicable state, local, and federal regulatory requirements. The Principal Investigator will assure that no deviation from, or changes to the protocol will take place without prior agreement from the Sponsor and documented approval from the Institutional Review Board (IRB), except where necessary to eliminate an immediate hazard(s) to the trial participants. An Operations Manual will be provided as a reference guide and study quality assurance tool.

16.3 Institutional Review Board Approval

This study will utilize a single IRB (sIRB). Prior to initiating the study, site investigators will obtain permission to rely on the MUSC IRB from their local IRBs. Local IRBs will enter into a reliance agreement with MUSC. Each participating site must have sIRB approval prior to conducting the study. Should changes to the study protocol become necessary, protocol amendments will be submitted in writing by the lead investigators for sIRB approval prior to implementation. In addition, the sIRB will approve all consent forms, and recruitment materials, and any study-specific materials given to the participant. Annual progress reports will be submitted to the sIRB annually or at a frequency requested so that continuous study approval is maintained without lapse. The lead investigator is responsible for maintaining in his research files copies of all performance site(s) current IRB/IEC approval notice(s), IRB-approved consent document(s), including approval for all protocol modifications. The lead site will submit regulatory documents to the sIRB on behalf of the participating sites. Participating sites will receive electronic notifications of approval or changes required directly from the sIRB. The lead team will also have access to all of these documents.

Prior to initiating the study, participating site investigators will obtain written approval from the single Institutional Review Board (sIRB) of record to conduct the study at their respective site, which will include approval of the study protocol. Approval of both the protocol and the consent form(s) must be obtained before any participant is consented. For changes to the consent form, a decision will be made regarding whether previously consented participants need to be re-consented. IRB continuing review will be performed annually, or at a greater frequency contingent upon the complexity and risk of the study. Each site principal investigator is responsible for

maintaining copies of all current IRB approval notices, IRB-approved consent documents, and approval for all protocol modifications. These materials must be received by the investigator prior to the initiation of research activities at the site, and must be available at any time for audit. Unanticipated problems involving risk to study participants will be promptly reported to and reviewed by the sIRB of record, according to its usual procedures.

MUSC Institutional Review Board will be the single IRB of record for the protocol, and will provide study oversight in accordance with 45 CFR 46 and applicable FDA regulations. Participating institutions have agreed to rely on MUSC Institutional Review Board, and will enter into reliance/authorization agreements for Protocol CTN-0108. MUSC Institutional Review Board will follow written procedures for reporting its findings and actions to appropriate officials at each participating institution. Some sites may meet Exception Criteria to the NIH sIRB Policy and may not utilize the IRB of Record.

